
Section 4.1.2 Secondary Endpoints p. 49-50 (Continued)
	
 Change in number of ‘other’ seizures (absence, myoclonic, partial sensory and infantile/epileptic spasms). Change in number of infantile/epileptic spasms. 
(...)
 
 Change in Tanner Staging score (for patients aged 10–17 [inclusive]). Quality of Life: 
(...)
	
improvement, 50–75% improvement or >75% improvement in TSC-associated seizure* frequency.
 
 Change in total seizures Change in composite focal seizure score (frequency × severity). Change in number of TSC-associated seizure*-free days. Change in number of seizures by subtype. Change in number of ‘other’ seizures (absence, myoclonic, focal sensory and infantile/epileptic spasms). 
(...)
 
 Change in Tanner Staging score (for patients aged 10–17 [inclusive]). 
Quality of Life:
 
(...)
	
See Section 2.10
 
See Section 2.10

Revised Protocol Section Number, Heading and Page Number	Original Wording from Clinical Protocol Version 2 Date 21 OCT 2015 (Deleted wording is struck through and in bold)	Revised Wording from Clinical Protocol Amendment 2 (Clinical Protocol V3 25Aug16) (Revised wording is underscored and in bold)	Rationale for the amendment
Section 4.1.2 Secondary Endpoints p. 50	
(...)
 
 • The plasma concentration/time curve of CBD, THC and their major metabolites will be described following single and multiple doses of GWP42003-P, with the aim being to estimate: 
 • Peak plasma concentration (C_{max}). • Time to peak concentration (t_{max}). • Area under the plasma concentration curve from time zero to infinity ($AUC_{0-\infty}$). • Terminal half-life ($t_{1/2}$). 	
(...)
 
 • The plasma concentrations will be summarized by time window for CBD and its major metabolites following single and multiple doses of GWP42003-P. Where data allows, the area under the plasma concentration curve (AUC_{0-t}) from time zero to the last measurable time-point will be calculated. 	See Section 2.4

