
Section 13.6.3 Secondary Endpoints p. 118-120
	
 Number of patients experiencing a >25% worsening, -25 to +25% no change, 25-50% improvement, 50-75% improvement or >75% improvement in seizure frequency. Change in composite focal seizure score (frequency × severity). Change in number of seizure-free days. Change in number of seizures by subtype. Change in number of ‘other’ seizures (absence, myoclonic, partial sensory and infantile/epileptic spasms). Change in number of infantile/epileptic spasms. 
(...) Blinded Phase: The number of patient responders and the number of patients’ seizure free will be summarized and analyzed using the difference in proportions and the odds ratio, together with 95% CIs, comparing the treatment groups. For changes in composite focal seizure score, number of
	
frequency.
 
 Number of patients experiencing a >25% worsening, -25 to +25% no change, 25-50% improvement, 50-75% improvement or >75% improvement in seizure frequency. Change in total seizures Change in composite focal seizure score (frequency × severity). Change in number of seizure-free days. Change in number of seizures by subtype. Change in number of ‘other’ seizures (absence, myoclonic, focal sensory and infantile/epileptic spasms). 
(...) Blinded Phase: The number of patient responders (including the key secondary endpoint) and the number of patients seizure free will be summarized and analyzed using a
	
See Section 2.6

Revised Protocol Section Number, Heading and Page Number	Original Wording from Clinical Protocol Version 2 Date 21 OCT 2015 (Deleted wording is struck through and in bold)	Revised Wording from Clinical Protocol Amendment 2 (Clinical Protocol V3 25Aug16) (Revised wording is underscored and in bold)	Rationale for the amendment

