Revised Protocol Section Number, Heading and Page Number	Original Wording from Clinical Protocol Version 2 Date 21 OCT 2015 (Deleted wording is struck through and in bold)	Revised Wording from Clinical Protocol Amendment 2 (Clinical Protocol V3 25Aug16) (Revised wording is underscored and in bold)	Rationale for the amendment

Section 13.6.3 Secondary Endpoints p. 118-120 (Continued)
	
and proportions. Number (%) of patients with changes in Tanner Stages will be summarized by treatment group.
 
The primary efficacy analysis uses the ITT analysis set over the evaluable period. ANCOVA analysis, using the LOCF approach, will be used to handle missing values.
 
In order to explore the robustness of the primary analysis, further sensitivity analysis (in addition to that already detailed in Section 13.6.2.1) may be specified in the SAP.
 
Similar approaches, using the LOCF, will be applied if the data are analyzed using non-parametric methods.
	
of seizures (average per 28 days) by subtype and the number of ‘other’ seizures (average per 28 days) will be analyzed using a Wilcoxon rank-sum test as per the primary endpoint.
 
SGIC-SD/CGIC-SD, SGIC/CGIC and PGIC assessments recorded at the end of treatment will be analyzed with ordinal logistic regression using the proportional odds model.
 
Changes from baseline for IGF-1 levels will be summarized by treatment group and plotted against the Tanner Stages, weight, and height.
 
Tanner Stages will be evaluated and summarized descriptively at each time point in terms of frequency and proportions. Number (%) of patients with changes in Tanner Stages will be summarized by treatment group.
 
In order to explore the robustness of the primary analysis, further sensitivity analysis (in addition to that already detailed in Section 13.6.2.1) may be specified in the SAP.
	
See Section 2.3

Revised Protocol Section Number, Heading and Page Number	Original Wording from Clinical Protocol Version 2 Date 21 OCT 2015 (Deleted wording is struck through and in bold)	Revised Wording from Clinical Protocol Amendment 2 (Clinical Protocol V3 25Aug16) (Revised wording is underscored and in bold)	Rationale for the amendment

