Section 1 PROTOCOL SYNOPSIS Procedures p. 14–19 (continued)	OLE visits will occur on Day 15, Day 29 , Day 85 and then every three months up to one year, then every six months thereafter until the end of treatment. (...) The following assessments will be completed at all visits during the OLE: 
 • Concomitant medication review (including AEDs) • AE review • Physical examination • Tanner Staging, where appropriate (Visits B2, B5 and subsequent Assessment Visits) 	titration. OLE visits will occur on Day 15, Day 36 , Day 92 and then every three months up to one year, then every six months thereafter until the end of treatment. (...) The following assessments will be completed at visits during the OLE (full listing by visit included in Section 9.1.2.): 
 • Concomitant medication review (including AEDs) • AE review • Physical examination • Tanner Staging, where appropriate (Visit B4 and subsequent Assessment Visits) 	
Section 1 PROTOCOL SYNOPSIS Statistical Considerations p. 19–20	(...) Each of the primary and secondary endpoints will be described and compared between treatment groups, using appropriate statistical methods, over the 15-week , double-blind maintenance and titration period. (...) Where baseline data are available from the Core study ,	(...) Each of the primary and secondary endpoints will be described and compared between treatment groups, using appropriate statistical methods, over the 16-week , double-blind maintenance and titration period. (...) Where baseline data are available from the blinded	See Section 2.11

Revised Protocol Section Number, Heading and Page Number	Original Wording from Clinical Protocol Version 1, Date 16 Jun 15 (Deleted wording is struck through and in bold)	Revised Wording from Clinical Protocol Amendment 1 (Clinical Protocol Version 2, Date 21 Oct 15) (Revised wording is underscored and in bold)	Rationale for the amendment
	changes from baseline will also be presented. (...)	phase , changes from baseline will also be presented. (...)	

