Revised Protocol Section Number, Heading and Page Number	Original Wording from Clinical Protocol Version 1, Date 16 Jun 15 (Deleted wording is struck through and in bold)	Revised Wording from Clinical Protocol Amendment 1 (Clinical Protocol Version 2, Date 21 Oct 15) (Revised wording is underscored and in bold)	Rationale for the amendment
	
cognitive and behavioral function compared with placebo.
 
 To evaluate the long term effect of GWP42003-P on growth and development (in patients less than 18 years old) compared with placebo. To evaluate the effect of GWP42003-P on autistic features compared with placebo. 
(...)
	
on TAND, including cognitive and behavioral function and autistic features compared with placebo.
 
 To evaluate the long term effect of GWP42003-P on growth and development (in patients less than 18 years old) compared with placebo. 
(...)
	

Section 4.1 Study Design p. 43
	
(...) Patients will complete a 4-week baseline period before they are randomized to receive either 25 mg/kg/day GWP42003-P, 50 mg/kg/day GWP42003-P or placebo.
 
Randomization will be stratified by age according to the following ranges: 2-6, 7-11, 12-17 years and 18+ years. (...) Clinic visits will occur for screening (Day -28), randomization (Day 1) and, on Days 15 and 29 during titration and on Days 43, 57 and 85 until the end of treatment (Day 113). Safety telephone calls will be completed every two days
	
(...) Patients will complete a 1-week screening period and a 4-week baseline period before they are randomized to receive either 25 mg/kg/day GWP42003-P, 50 mg/kg/day GWP42003-P or placebo.
 
Randomization will be stratified by age according to the following ranges: 1-6, 7-11, 12-17 years and 18+ years. (...) Clinic visits will occur for screening (Day -35), baseline (Day -28), randomization (Day 1) and, on Days 15 and 29 during titration and on Days 43, 57 and 85 until the end of treatment (Day 113). Safety telephone calls will be completed every two days
	
See Section 2.3
 
See Section 2.5

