Section 9.1.1.3 Visit 3 (Day 1, Randomization) p. 63–64 (continued)	
examination (including height and body weight), ECG, vital signs, epilepsy-related hospitalizations and AEs.
 
Clinical laboratory samples (blood and urine [where possible]) will be taken for hematology, biochemistry and urinalysis.
 
(...) The PGIC, SGIC/CGIC and Vineland-II will also be performed.
	
examination (including height and body weight), details of menstruation (for females), Tanner Staging (for patients aged 10–17 years [inclusive], or earlier if clinically indicated by onset of menarche or other signs of precocious puberty), ECG, vital signs, postural blood pressure, epilepsy-related hospitalizations, AEs and paper diary review. The ECG will be repeated four hours after the first dose of IMP. The investigator will verify that the ESC has confirmed the diagnosis of TSC.
 
Clinical laboratory samples (blood and urine [where possible]) will be taken for hematology, biochemistry, urinalysis, a urine THC screen, determination of serum IGF-1 levels (for patients less than 18 years of age) and a pregnancy test if appropriate (using both a serum sample and a urine dipstick).
 
(...) PK samples (patients >20 kg in weight only) will be taken following randomization and at two hours and
	

Revised Protocol Section Number, Heading and Page Number	Original Wording from Clinical Protocol Version 1, Date 16 Jun 15 (Deleted wording is struck through and in bold)	Revised Wording from Clinical Protocol Amendment 1 (Clinical Protocol Version 2, Date 21 Oct 15) (Revised wording is underscored and in bold)	Rationale for the amendment

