- Physical examination (including height and body weight)
- 12-lead electrocardiogram (ECG)
- Vital signs
- Epilepsy-related hospitalizations
- AEs
- Subject Global Impression of Change in Seizure Duration (SGIC-SD)/Caregiver Global Impression of Change in Seizure Duration (CGIC-SD)
- Suicidality, assessed in accordance with Section 9.2.12.8 of the main protocol

At each assessment visit, clinical laboratory samples (blood and urine [where possible]), including a pregnancy test if appropriate (using both a serum sample and a urine dipstick), will be taken for hematology, biochemistry, urinalysis, and determination of serum insulin-like growth factor-1 (IGF-1) levels (for patients less than 18 years of age) to be performed by the central laboratory. Provided that the risk/benefit outcome is favorable in the investigator's opinion, prior to the first daily dose of IMP, a blood sample will be taken for analysis of plasma concentrations of concomitant AEDs.

The investigator must assess adherence to the dosing regimen by reviewing the patient's diary and IVRS data, record the patient's attendance at the visit, and confirm the outcome of the visit.

All IMP (used and unused) will be collected and a check of the returned IMP against usage should be made. Patients/caregivers will then receive sufficient IMP until the next scheduled visit.

In addition to the above, the following assessments will be made at Visit B18 and Visit B24:

- Details of menstruation (for females)
- Tanner staging (patients aged 10–17 [inclusive] only)
- Quality of Life in Childhood Epilepsy (QOLCE)/Quality of Life in Epilepsy (QOLIE-31-P)
- Subject Global Impression of Change (SGIC)/Caregiver Global Impression of Change (CGIC)
- Physician Global Impression of Change (PGIC)
- Wechsler Tests
- Child Behavior Checklist (CBCL)/Adult Behavior Checklist (ABCL)
- Social Communication Questionnaire (SCQ)
- Vineland Adaptive Behavior Scales, Second Edition (Vineland-II)

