6 DATA ANALYSIS

6.1 Patients to Analyze

Patients in the US who continue to participate in years 2, 3, and 4 of the OLE will be analyzed in accordance with the statistical considerations detailed in Section 13 of the main protocol.

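### In the uncontrolled extension, raw change in IGF-1 cannot separate normal maturation from a drug effect on growth, and the growth objective there names a placebo comparison that does not exist

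*Protocol*

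**What the plan says.** - **Objective.** Section 2.2 sets this for the extension: "To evaluate the long term effect of GWP42003-P on growth and development (in patients less than 18 years old". The sentence goes on to name placebo as the comparator.
- **Endpoint.** The Section 13.6.3 list marks some entries as extension-only or blinded-only, so it covers both phases. Under growth and development in patients under 18 it names change in serum IGF-1 level and change in Tanner score.
- **Analysis rule.** "Changes from baseline for IGF-1 levels will be summarized by treatment group and plotted against the Tanner Stages, weight, and height". This sentence belongs to the block that opens "Blinded Phase: The number of patient responders". The same block gives several other endpoints an age adjustment (an age-stratified Cochran–Mantel–Haenszel test, or ANCOVA with age group as covariate). IGF-1 gets none.
- **Extension.** The synopsis (Statistical Considerations) says that, where blinded-phase baseline data exist, "changes from baseline will also be presented". Section 6.1 of both annexes says that patients in the added years "will be analyzed in accordance with the statistical considerations detailed in Section 13 of the main protocol".
- **Sampling.** IGF-1 is drawn in patients under 18 at Visits B1 and B10 and at every annex assessment visit.
- **Tanner staging.** The Visit 3 text, repeated at Visit 10, provides for "Tanner Staging (for patients aged 10–17 years [inclusive], or earlier if clinically indicated by onset of menarche or other signs of precocious puberty". The endpoint in Section 4.1.2 is "Change in Tanner Staging score (for patients aged 10–17 [inclusive". Visit B10 also gives ages 10–17, and Section 4.3 of the US annex has "Tanner staging (patients aged 10–17 [inclusive] only".

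**The concern.** Enrolment starts at age 1, so IGF-1 is followed in patients aged 1–17. The plan's choice of plot axes (Tanner stage, weight, height) shows that its authors expected IGF-1 to move with maturation. A raw change over one to four years then contains whatever the child would have gained or lost by growing older, plus any effect of the drug.

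With a concurrent placebo group the first part cancels. The extension has no such group. Grouping by the original randomised arm does not restore one, because former placebo patients also move to active drug.

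At stake is the long-term growth objective. A cohort drifting below its age norm could still show a flat or rising mean level, and nothing in the visible rule would bring that to light. The objective's placebo wording adds to the problem by promising a contrast that the design cannot supply.

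**Working it through.** The documents state no expected change, SD or power for IGF-1, so there is no figure to reproduce. The check is of the mechanism.

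**Inputs from the documents.** The blinded phase lasts 16 weeks. The extension ends at week 52 (Visit B10), at up to week 156 in Poland and at up to week 208 in the US, all counted from Visit B1. The synopsis refers changes to the blinded-phase baseline, so 16 weeks are added to each.

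**Inputs assumed.** *g* is the normal yearly rise in IGF-1, taken as 0, 5, 10 and 20%. *f* is a proportional drug-related fall. Neither is in the documents.

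**Formulas**, with *t* in years from baseline:
- Raw change on active drug = (1+g)^t × (1−f) − 1
- Raw change on placebo = (1+g)^t − 1
- Ratio of active to placebo = 1 − f, whatever *g* is
- Largest fall that still leaves raw change at or above zero = 1 − (1+g)^(−t)

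| Time point | t (years) | g = 0% | 5% | 10% | 20% |
|---|---|---|---|---|---|
| End of blinded phase | 16/52 = 0.308 | 0 | 1.5% | 2.9% | 5.5% |
| Extension year 1 | 68/52 = 1.308 | 0 | 6.2% | 11.7% | 21.2% |
| Poland, year 3 | 172/52 = 3.308 | 0 | 14.9% | 27.0% | 45.3% |
| US, year 4 | 224/52 = 4.308 | 0 | 19.0% | 33.7% | 54.4% |

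Two cells in full: 1.05^1.308 = 1.066, and 1 − 1/1.066 = 6.2%. Likewise 1.20^4.308 = 2.193, and 1 − 1/2.193 = 54.4%.

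**One case followed through**, with g = 10% and f = 20%. At 16 weeks the active-to-placebo ratio shows the whole 20% fall. At US year 4 the raw change is 1.508 × 0.80 − 1 = +20.6%, a rise, although the patients are 20% below where they would otherwise be.

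**Tanner passages side by side.** Visits 3 and 10 allow staging below age 10 on clinical signs. The endpoint, Visit B10 and the assessment and end-of-treatment visits in both annexes give ages 10–17; the annexes add that it is those ages only. The Section 13.6.3 sentence that summarises Tanner stages at each time point sets no age limit. These do not describe one population.

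**The case against.** The other side has several good arguments.

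- The IGF-1 sentence is a blinded-phase rule. There, age-stratified randomisation against placebo balances normal growth and the contrast masks nothing. This stands in full.
- The extension block of Section 13.6.3 is not in the text available, and the synopsis line is general and does not name IGF-1. This stands as a limit: use of raw change in the extension is inferred from the endpoint definition and the annex cross-references.
- IGF-1 is only summarised, with no test or decision rule, and the choice of a standardised scale is often left to the SAP. It is true that a missing score would not by itself be a fault. But the protocol does fix the measure as change in level for both phases, and an SAP cannot supply the placebo comparator that the extension objective names.
- Plots against Tanner stage, weight and height, and the continued collection of all three, give some protection. That is partly right. A plot is not an adjustment, and age is not one of the axes.

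Two stronger readings are tempting and not supported. A reader might infer that a rise in mean raw IGF-1 would be reported as showing no growth concern; no document says how the summary will be interpreted. A reader might also infer that children staged before age 10 are lost from the analysis; the Tanner summary sentence carries no age limit, so that is not shown.

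**Conclusion.** The point holds for the extension and not for the blinded phase. Over 1 year, and up to 3 in Poland and 4 in the US, raw change in patients aged 1–17 cannot separate maturation from a drug effect and could mask a fall against the age norm.

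The size is unknown. It rests wholly on the assumed yearly rise: zero masking at 0%, and about 6–21% at the end of extension year 1 and 19–54% at US year 4 for 5–20% a year compounded without change. These are illustrations of what could be hidden, not estimates of harm.

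The placebo wording of the extension objective is an inconsistency on the face of the text and needs no assumption. The Tanner mismatch is a separate matter of wording between passages. None of this touches the primary endpoint. The change should be made because it is cheap and the long-term growth objective depends on it.

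**What to change.** 1. In Section 13.6.3, for extension and annex data, summarise IGF-1 as change in age- and sex-standardised score from the central laboratory's reference ranges, with the number of patients below −2, and keep raw values alongside. The annexes pick this up through their reference to Section 13.
2. Do the same for the height and weight already measured, against a named growth reference.
3. Reword the extension growth objective so that it no longer claims a comparison with placebo.
4. Reconcile the Tanner passages (Visits 3 and 10, the Section 4.1.2 endpoint, Visit B10 and both annexes) so that the staged and analysed populations agree. Which age rule applies is for the sponsor to settle. Do not impute stages for children who were not staged.

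The cost of items 1 to 3 is wording plus a derivation from age, sex, height, weight and IGF-1 already collected, with no extra samples. The downside is reliance on the laboratory's reference ranges, which must be available by age and sex. Whether item 4 adds any staging depends on how the passages are reconciled.

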APPENDIX 1 AMENDED FIGURES AND TABLES

Amended Figure from Clinical Protocol V3 25Aug16

[figure not shown]
(Deleted wording is struck through and in bold; amended wording is underlined and in bold)

Amended Figure 1.1 Study Design and Treatment Schema: Blinded Phase

[figure not shown]
Original Figure from Clinical Protocol Version 2, Date 21 OCT 2015
(Deleted wording is struck through and in bold; deleted lines are in bold and dashed)

Original Figure 1.2 Study Design and Treatment Schema: Open-label Extension

Amended Figure from Clinical Protocol V3 25Aug16
(Amended wording is underlined and in bold)

Amended Figure 1.2 Study Design and Treatment Schema: Open-label Extension

Original Table from Clinical Protocol Version 2, Date 21 OCT 2015
(Deleted wording is struck through and in bold)

Table 9.1.2.6.1 OLE Visit Schedule		
Visit Number	Visit Type	Time from Visit B1 (except where indicated)
B5	Re-supply	7 weeks from B4 (± 7 days)
B6	Assessment	26 weeks (± 7 days)
B7	Re-supply	7 weeks from B5 (± 7 days)
B8	Assessment	39 weeks (± 7 days)
B9	Re-supply	7 weeks from B7 (± 7 days)
B10	Assessment	52 weeks (± 7 days)
B11	Re-supply	9 weeks from B9 (± 14 days)
B12	Re-supply	18 weeks from B9 (± 14 days)
B13	Assessment	78 weeks (± 14 days)
B14	Re-supply	9 weeks from B12 (± 14 days)
B15	Re-supply	18 weeks from B12 (± 14 days)
B16	Assessment	104 weeks (± 14 days)
Continue sequentially	Assessment	Continue every 6 months (± 14 days)
Continue sequentially	Re-supply	Continue every 7-11 weeks between Assessment Visits

Original Schedule of Assessments (Blinded Phase) from Clinical Protocol Version 2, Date 21 OCT 2015
(Deleted wording is struck through and in bold; deleted lines are in bold and dashed)

Blinded Phase

Visit Number	1	2	3	4	5	6	7	8	9	10	11	12 (Tel.)	Safety Calls*
Informed consent/assent	X												
Eligibility Criteria	X	X	X										
Randomization			X										
Demographics	X												
Medical history	X												
Vital signs	X		X	X	X	X	X		X	X	X		
Postural BP	X		X										
Physical examination (including height and body weight)	X		X	X	X	X	X		X	X	X		
ECG	X		X	X	X	X	X		X	X	X		
Clinical laboratory blood sampling	X		X	X	X	X	X		X	X	X		
Clinical laboratory urine sampling (dipstick urinalysis)	X		X	X	X	X	X		X	X	X		
Urine THC screen	X		X							X			
Pregnancy test (if appropriate)	X		X							X			
Pharmacokinetic blood sampling [♦]			X							X			
AED concentration			X		X		X		X	X			
AEs	X	X	X	X	X	X	X	X	X	X	X	X	X
Concomitant medications	X	X	X	X	X	X	X	X	X	X	X	X	X
Inpatient epilepsy-related		X	X	X	X	X	X	X	X	X	X	X	X

Visit Number	1	2	3	4	5	6	7	8	9	10	11	12 (Tel.)	Safety Calls*
hospitalizations													
Suicidality / C-SSRS/Children's C-SSRS	X		X	X	X	X	X		X	X	X		
Vineland-II			X							X			
SGIC/CGIC			X	X	X	X	X		X	X			
PGIC			X	X	X	X	X		X	X			
SGIC-SD/CGIC-SD			X							X			
QOLCE/QOLIE-31-P			X							X			
Wechsler Tests			X							X			
CBCL/ABCL			X							X			
SCQ			X							X			
Tanner Staging (where appropriate) and IGF-1 testing			X							X			
Menstruation question (where appropriate)			X							X			
Patient diary review (seizures, AE information, concomitant AEDs, rescue medication, IMP dosing)			X	X	X	X	X		X	X	X		
IVRS and diary training		X											
IMP dispensing			X	X	X	X	X		X	X			
Collection of IMP				X	X	X	X		X	X	X		
IMP compliance review				X	X	X	X		X	X	X		
Study Medication Use and Behavior Survey										X			

Amended rows of Schedule of Assessments (Blinded Phase) from Clinical Protocol V3 25Aug16
(Amended wording is underlined and in bold)

Blinded Phase

Visit Number	1	2	3	4	5	6	7	8	9	10	11	12 (Tel.)	Safety Calls*
Day	-35	-28	1	15	29	43	57	71	85	113	123	151	
Visit Window		±7	+3	±3	±3	±3	±3	±3	±3	±3 [∞]	+3	+3	
(...)													
Vital signs and BP	X		X	X	X	X	X		X	X	X		
Postural BP	X		X		X								
(...)													
Urine/ serum THC screen	X												
Pregnancy test (if appropriate)	X		X		X		X		X	X			
(...)													
TSC1 and TSC2 mutation status	X												
(...)													
Inpatient epilepsy-related hospitalizations	X	X	X	X	X	X	X	X	X	X	X	X	X

Visit Number	1	2	3	4	5	6	7	8	9	10	11	12 (Tel.)	Safety Calls*
Day	-35	-28	1	15	29	43	57	71	85	113	123	151	
Visit Window		±7	+3	±3	±3	±3	±3	±3	±3	±3 [∞]	+3	+3	
Suicidality / C-SSRS/Children's C-SSRS	X		X	X	X	X	X		X	X	X		
(...)													
SGIC/CGIC			X							X			
PGIC			X							X			
(...)													

Original Schedule of Assessments (OLE Phase) from Clinical Protocol Version 2, Date 21 OCT 2015
(Deleted wording is struck through and in bold; deleted lines are in bold and dashed)

Visit Number	B1	B2	B3	B4	Assessment Visits (B6, B8)	Re-Supply Visits (B5, B7, B9)	End of Treatment	End of Taper	Follow up (Tel)	Safety Calls*
Informed consent/assent	X									
